The purpose of the present study is to evaluate this potential, using AI. It will conduct an interview with standardized SP patients (actors) presenting a psychiatric illness, and based on the interview, it will present a differential diagnosis and treatment plan. Immediately afterwards, the actors will be interviewed by a board certified psychiatrist, who will also give a differential diagnosis and a treatment plan. The results of the AI and psychiatrist will be compared. In the second part of the study, AI will examine patients coming for consultation by a psychiatrist in the inpatient units, outpatient units or in the emergency room (ER) in Sheba. The patient will give informed consent, and will be interviewed by AI. The interview will be done either digitally, or will use to voice-to-text and text-to-voice technology that will allow the patient to speak with the computer, instead of typing questions into the computer. Future studies, not included in the current proposal, will use voice analysis, face recognition and computerized emotion recognition as part of AI.

Methods

Participants:

1. Five actors SPs, each time employed by MesserMSR, the Israeli Center for Medical Simulation, trained to simulate symptoms of psychiatric illnesses.
2. Patients (n=200) treated in the Division of Psychiatry in the Sheba Medical Center. In addition, patients who applied for treatment in the psychiatric clinic in the Division of Psychiatry in the Sheba Medical Center but are not yet treated there, and patients treated in the psychiatric emergency room (ER) in Sheba. In addition, a recruitment ad will be published in the media and on social networks, to include patients who will come in specifically to participate in the study.
3. Ten board certified Psychiatrists from the Drora and Pinchas Zachai Division of Psychiatry in the Sheba Medical Center.

Scenarios for actors:

The actors will be trained in one of 5 scenarios: depression, anxiety, PTSD with cannabis abuse, psychosis and control patient with no diagnosis. Each scenario will have 2 levels of severity. The actors will present demographic and medical background, symptoms and signs, including disorders of thought and affect.

Procedure:

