Actors or patients will be interviewed by AI. The interview will either be digital or will utilize AI voice to text and text to voice technology, so that the participant will be speaking with the application which will respond vocally. After the AI interview the participant will be interviewed by a board-certified psychiatrist, who will determine the differential diagnosis and recommend treatment. Both, the AI and the psychiatrist, interviews will be audiotaped. The entire procedure will be repeated twice, for two days. After that, technological improvements will be made in AI. For the third time, the SPs will play against the AI only to check that the technological changes made didn't harm the quality of the AI.

Proposed schedule for actors

Time line		AI session 1

	1	Depression Low severity	Anxiety Low severity	PTSD with cannabis abuse Low severity	Psychosis Low severity	Control patient
	2	Depression High severity	Anxiety High severity	PTSD with cannabis abuse High severity	Psychosis High severity	Control patient
		Face to face phase *				
		Doctor 1		Doctor 2	Doctor 3	Doctor 4
	3	Depression Low severity	Anxiety High severity	PTSD with cannabis abuse Low severity	Psychosis Low severity	Control patient
	4	Psychosis High severity	Depression Low severity	Anxiety Low severity	PTSD with cannabis abuse Low severity	Control patient
	5	PTSD with cannabis abuse High severity	Psychosis Low severity	Depression High severity	Anxiety High severity	Control patient
	6	Anxiety Low severity	PTSD with cannabis abuse High severity	Psychosis High severity	Depression High severity	Control patient
		AI session 2 **				
	7	Depression High severity	Anxiety High severity	PTSD with cannabis abuse High severity	Psychosis High severity	Control patient
	8	Depression Low severity	Anxiety Low severity	PTSD with cannabis abuse Low severity	Psychosis Low severity	Control patient

* We can choose any other balance of disorder and severity between doctors.

** two AI sessions to overcome the question per hour limit.

*** We will set the exact schedule prior to the training. The study should take half a day. 3:30-4 hour day.

For the actor's part of the project, over all there will be 125 encounters, 75 with AI and 50 with a psychiatrist in 3 days. The interviews of the actors and psychiatrist in MSR will be videotaped, so that in the future voice and facial analysis can be integrated into the project.

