"Artificial intelligence to be used as a diagnostic tool in mental health and recommendations for a treatment plan."

As part of this study, we are recruiting men and women over the age of 18. The main purpose of the study is to compare the results of the AI system test with the results of a psychiatrist's examination.

Participation in the study includes arriving at the Sheba Tel Hashomer Hospital for examination by the AI system and a psychiatrist. It will be possible to receive the summary of the meeting with the psychiatrist. Expenses will be reimbursed in the amount of NIS 100.

The details of the subjects will be kept confidential

Those interested in participating are welcome to send a text/WhatsApp message

[contact]

In addition, all participants in the study will be asked to fill out a satisfaction questionnaire (attached Appendix 1). And the examining psychiatrists will be asked to fill out a form of diagnosis, severity and recommendations for drug and psychotherapeutic treatment (attached in Appendix 2). This interview will be audiotape.

The primary outcome of the study will be a comparison of the interviews, differential diagnoses and recommendations for treatment assigned by the AI with those assigned by the board certified psychiatrist. the rates of agreement will be the outcome of interest.

All actors, patients, and psychiatrists participating (The psychiatrists who participate in the actors part) will give informed consent.

security and privacy:

1-Actors in MSR: The interviews will be recorded and stored in the Simboost server managed by MSR.

2-Patients in the Division of Psychiatry and ER: after giving informed consent, the investigators will enter the patients ID number into a conversion table, so that each patient will receive a code number which will identify the patient for AI.

The conversion table and the audiotape interviews will be stored in the Sheba secured server, which be accessed only by the research team.

Statistical Analysis Plan

Data

Actors who simulate one of four psychiatric illnesses (anxiety, depression, PTSD, or Mania) or a control condition that is not considered psychotic) are interviewed by a psychiatrist or a computerized AI program (called Liv), and for each interview the following is recorded:

- (i) Interviewer (psychiatrist or Liv)
- (ii) If psychiatrist, identity number
- (iii) True diagnosis
- (iv) True severity (mild/severe)
- (v) Medication indicated
- (vi) Psychiatric treatment indicated

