- (vii) Primary diagnosis made
- (viii) Secondary and Tertiary diagnoses made
- (ix) Severity (mild/moderate/severe)
- (x) Medications recommended
- (xi) Psychiatric treatment recommended

The codes 0, 5 (no diagnosis) and 9 (adjustment disorder) are taken to be equivalent diagnoses in the analyses described below.

Analyses

Note that in the analyses below, all estimated percentages will be accompanied by a 95% confidence interval.

- (a) Diagnosis:

The overall results will be summarized as:

1. % agreement of the primary diagnosis with gold standard over all conditions: (i) for Liv; (ii) for psychiatrists.
2. % agreement between Liv and psychiatrists; this calculation will need a special method – see paragraph (f) below.
3. The results will be displayed also as cross-tabulations of the 5 conditions according to gold standard versus Liv, according to gold standard versus psychiatrists, and according to psychiatrists versus Liv.
4. Analyses 1, 2, and 3 above will be repeated under the rule that agreement with the gold standard is achieved if one of the diagnoses (primary, secondary or tertiary) agrees with the gold standard, and agreement with the psychiatrists is achieved if one of the Liv diagnoses (primary, secondary or tertiary) agrees with the primary diagnosis of the psychiatrist.

(b) Diagnosis according to severity of condition:

The following analyses will be conducted:

5. As in 1 and 2 above, but for severe conditions only.
6. As in 1 and 2 above, but for mild/moderate conditions only.
7. As in 3 above, but for severe conditions only.
8. As in 3 above, but for mild/moderate conditions only.
9. As in 4 above, but for severe conditions only.
10. As in 4 above, but for mild/moderate conditions only.

(c) Diagnosis and Severity:

Note that throughout, **mild and moderate severity assessments will be considered equivalent**. If the psychiatrist or Liv classifies a patient with mild severity as having moderate severity, this will not be counted as an error.

Severity assessments will be evaluated in two different ways:

First, they will be included as part of the definition of a correct classification: e.g. a patient with severe anxiety will be considered correctly classified only if the psychiatrist or Liv classifies them as having severe anxiety. A classification of mild/moderate anxiety will be counted as an error. Analyses using this type of evaluation are listed below.

11. As in 1 and 2 above.

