12. As in 3 above, but here the table will be a 9 x 9 cross-classification, with the following categories: mild anxiety, severe anxiety, mild depression, severe depression, mild PTSD, severe PTSD, mild Mania, severe Mania, control.

Second, **within the set of correctly assigned primary diagnoses**, we will do the following analyses:

13. % agreement of assigned severity scores with the gold standard (i) for Liv and (ii) for psychiatrists.

14. % agreement of assigned severity scores by Liv versus that assigned by the psychiatrists.

15. The results will be displayed also as 2 x 2 cross-tabulations of the 2 severities according to gold standard versus Liv, according to gold standard versus psychiatrists, and according to psychiatrists versus Liv.

(d) Medications and psychiatric treatments:

Agreement of the recommendations provided by Liv and by the psychiatrists will be compared with the gold standard. As with the second approach to evaluating severity assessments, the comparisons will be made only **within the set of correctly assigned primary diagnoses**.

There will be only one primary gold standard medication (psychiatric treatment), and the recommendation by Liv or the psychiatrist will be judged correct only if it includes this primary medication (psychiatric treatment).

Thus the two main analyses will be:

16. % agreement with primary gold-standard medication of (i) Liv's recommended medication and (ii) psychiatrists' recommended medication.

17. % agreement with primary gold-standard psychiatric treatment of (i) Liv's recommended treatment and (ii) psychiatrists' recommended treatment.

(e) Decision thresholds:

On the basis of certain of the above statistics, we specify two conditions that must be satisfied for Liv to proceed to the Phase II study that involves real patients arriving for diagnosis and treatment at Sheba Medical Center.

A. The % agreement of the psychiatrists' primary diagnosis with the gold standard is >85%.

If it falls below this value, then it will be concluded that the "simulation" was not sufficiently realistic and some adjustments to the training of the actors will need to be made.

B. The % agreement of Liv's primary diagnosis with the psychiatrists' primary diagnosis >85%. If it falls below this value, then it will be concluded that adjustments are required to the Liv program.

Reference

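### A 95% interval is promised for every percentage with no method for repeated plays of nine scripts, and the listed data cannot separate Liv before and after it is modified

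*Combined protocol and SAP*

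**What the plan says.** The SAP (Analyses, opening note) states that "all estimated percentages will be accompanied by a 95% confidence interval". It gives no interval method, no variance model and no rule for repeated measurements.

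The structure of the data comes from Methods and the schedule:

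- Participants: "Five actors SPs, each time employed by MesserMSR". The words leave open whether the same five return on each day.
- Scenarios: "The actors will be trained in one of 5 scenarios: depression, anxiety, PTSD with cannabis abuse, psychosis and control patient with no diagnosis", and "Each scenario will have 2 levels of severity". Read literally that is ten scripts. The printed schedule gives the control one level, and SAP analysis 12 says "the table will be a 9 x 9 cross-classification", so the working number is nine. (Methods lists psychosis where the SAP lists mania; the count is the same.)
- Encounters: "75 with AI and 50 with a psychiatrist in 3 days".
- Procedure: Liv and psychiatrists both interview on two days. Liv is then modified, and a third, AI-only day checks that the modification did no damage.

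The SAP's data list, items (i)-(xi), holds interviewer type, psychiatrist identity ("ii) If psychiatrist, identity number"), true diagnosis, true severity, the indicated treatments and the assessments made. It has no field for actor, day or session, or Liv version. Psychiatrist identity appears in none of the listed analyses.

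Decision thresholds A and B in SAP paragraph (e) each compare a percentage with 85%. For Liv-psychiatrist agreement, analysis 2 defers to a special method in a paragraph (f); the SAP text ends at (e).

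**The concern.** The percentages are computed over encounters, but encounters are not separate test cases. A script played repeatedly by the same actor tends to be diagnosed correctly, or missed, for the same reasons each time, and each psychiatrist contributes several interviews. If the statistician falls back on a binomial interval, its width answers a question that the SAP has not posed: is the target agreement on these nine scripts, or on the kind of presentation that they represent? The result feeds a decision to move to real patients, so a reader will be inclined to take it in the second sense.

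The version problem is distinct and needs no correlation model. Analysis 1(i) asks for one agreement percentage for Liv. With Liv modified before day 3 and no version or day field, that percentage can mix two programs, and the listed data cannot show whether the modified one is better or worse. That comparison is the purpose of the third day.

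**Working it through.** **1. The plan's own counts.** The stated total is 75 + 50 = 125, which fits 25 encounters per interviewer type per day (25 × 3 and 25 × 2), although 25 is not stated. The printed schedule has four AI rows and four face-to-face rows of five, so 20 × 3 = 60 and 20 × 2 = 40. It is marked as provisional, so I do not call 125 wrong. I use 75 and 50, and test 40 in step 3.

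**2. Scripts.** 4 conditions × 2 severities + 1 control = 9.

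**3. Condition A, psychiatrists against gold standard.** Inputs: n = 50 (Procedure), p = 0.85 (the threshold), k = 9 clusters. The intraclass correlation (ICC) is not in the documents; I assume 0 to 0.3.

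Design effect DE = 1 + (m − 1) × ICC, with m = 50/9 = 5.56. Half-width = 1.96 × √(0.85 × 0.15 × DE / n).

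| ICC | DE | Effective n | Half-width (points) |
|---|---|---|---|
| 0 | 1.00 | 50 | 9.9 |
| 0.1 | 1.46 | 34.4 | 11.9 |
| 0.3 | 2.37 | 21.1 | 15.2 |

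- Unequal script sizes: the face-to-face rows give the control 4 of 20 slots and each other script 2. At n = 50 that is 10 and 5, so m = (10² + 8 × 5²)/50 = 6, DE is 1.5 and 2.5, and the half-widths become 12.1 and 15.6.
- With the schedule's n = 40 and m = 40/9 = 4.44, the three half-widths are 11.1, 12.8 and 15.8.
- A t reference with 8 df in place of 1.96 would widen the clustered figures further.

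**4. Coverage.** In a beta-binomial simulation (100,000 runs, true agreement 85%, n = 50, nine clusters), a nominal 95% Wilson interval that assumes independence covers 95.5% at ICC 0, 90.5% at 0.1 and 80.5% at 0.3.

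**5. The other direction: conditions as fixed strata.** The sampling variance is then the mean of p(1 − p) over strata.

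- Rates 1, 1, 1, 0.9, 0.35 (mean 0.85): (0.09 + 0.2275)/5 = 0.0635 against 0.1275, ratio 0.50. Simulated Wilson coverage is 99.6%, so the interval is too wide.
- Rates 0.95, 0.90, 0.85, 0.80, 0.75: 0.1225/0.1275 = 0.96, coverage 96.1%. Almost no effect.

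**6. Liv against gold standard, n = 75.** With m = 75/9 = 8.33 the half-widths are 8.1, 10.6 and 14.5 points at ICC 0, 0.1 and 0.3. No threshold is set on this percentage.

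**7. Pooling versions.** Take 50 encounters before the change and 25 after.

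- 80% then 96%: (40 + 24)/75 = 64/75 = 85.3%.
- 92% then 72%: (46 + 18)/75 = 64/75 = 85.3%.

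A 16-point gain and a 20-point loss give the same figure, and items (i)-(xi) contain nothing to tell them apart.

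**The case against.** Four stronger readings are tempting, and the documents do not support them.

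- *The go/no-go decision rests on faulty intervals.* It does not. A and B compare point estimates with 85%, and no confidence limit enters the rule.
- *The intervals will be too narrow.* The SAP never says that it will use an independent-binomial interval. The conditions and severities were chosen, not sampled, and failing condition A leads to changes in actor training, so inference conditional on these scripts is a natural reading there. Under it the error can vanish or reverse (step 5).
- *The n = 75 half-widths show how uncertain the thresholds are.* They belong to Liv against gold standard. Condition B is Liv against psychiatrists; its denominator is undefined and its calculation is assigned to paragraph (f), so no interval for it can be worked out here.
- *The listed data cannot support clustering at all.* Script can be rebuilt from items (iii) and (iv), psychiatrist is item (ii), and actor equals condition if each actor keeps one role. Actor is lost only if actors change or swap roles.

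It can also be said that no interval over nine chosen scripts carries over to real patients, and that the 200-patient part addresses that. This is true. It is a reason to label the interval properly, and it leaves the choice of method still to be made. The objection does not touch the missing day and version fields. The interviews are recorded, so dates may perhaps be traceable, but the SAP names no link from recordings to the analysis data.

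**Conclusion.** The concern stands in limited form. The SAP should name an interval method suited to repeated plays of nine scripts; an interval that assumes independent encounters is likely to misstate precision, in a direction that depends on whether scripts and actors are treated as a sample or as fixed. For condition A the half-width runs from 9.9 points under independence to 11.9 and 15.2 under assumed ICCs of 0.1 and 0.3. Those ICCs are illustrations; the true size cannot be found from the documents and may be negligible. The consequence is for how firmly an 85% result is read, not for whether the rule is met.

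The version point is firmer because it rests on no assumed correlation: with neither day nor Liv version in items (i)-(xi), analysis 1(i) can pool two programs and the day-3 check cannot be made from the listed data. It concerns Liv's percentages and does not affect condition A. The change should be made before data collection, since day and version may be hard to reconstruct later.

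**What to change.** 1. Add actor ID, day or session, and Liv version to the recorded items.
2. Report Liv's percentages by version, and state which version condition B uses.
3. For the overall percentages in analysis 1, keep the encounter-weighted percentage and give a script-clustered interval with a small-sample correction (t reference, 8 df). Take psychiatrist identity into account for the psychiatrist percentages. Show the simple binomial interval beside it, labelled as conditional on these scripts.
4. For analyses 5-10 and 13-17, which have too few scripts or are confined to correctly diagnosed encounters, label the intervals as descriptive and conditional on the scripts.
5. For Liv-psychiatrist agreement, supply paragraph (f) and make the interval consistent with its method.

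Two alternatives are best avoided. An unweighted mean of nine script rates changes the quantity: with the control at 100% and the other eight scripts at 82%, the encounter percentage is 0.2 × 100 + 0.8 × 82 = 85.6%, but the script mean is (100 + 8 × 82)/9 = 84.0%, on the other side of the threshold. An uncorrected GEE, or a crossed random-effects model, would be fragile with nine clusters and about seven errors (50 − 43, at the smallest passing result of 43/50).

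The cost is a few data columns, some SAP wording and a little analysis work. The reported intervals will probably be wider.

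### No listed SAP item computes Liv-versus-psychiatrist agreement on treatment, although the primary outcome includes it

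*Combined protocol and SAP*

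**What the plan says.** The primary-outcome paragraph of the protocol (Methods, Procedure) compares the interviews, the diagnoses and the "recommendations for treatment assigned by the AI with those assigned by the board certified psychiatrist. the rates of agreement" are then named as the quantity of interest. The comparator there is the psychiatrist, and treatment is named explicitly.

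Section (d) of the SAP, on medications and psychiatric treatments, sets a different comparator: "Agreement of the recommendations provided by Liv and by the psychiatrists will be compared with the gold standard". Item 16 reports the percentage "agreement with primary gold-standard medication of" Liv and, separately, of the psychiatrists. Item 17 does the same for psychiatric treatment. A recommendation counts as correct if it includes the single gold-standard item. Both items are confined to interviews "within the set of correctly assigned primary diagnoses". Section (d) introduces them as the two *main* analyses and lists no others.

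Elsewhere the SAP does list direct comparisons. Item 2 does so for diagnosis, with its method deferred ("see paragraph (f) below"). Item 4 adds a looser rule: "agreement with the psychiatrists is achieved if one of the Liv diagnoses (primary, secondary or tertiary) agrees with the primary diagnosis of the psychiatrist". Item 14 covers severity: "agreement of assigned severity scores by Liv versus that assigned by the psychiatrists".

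The SAP's Data section describes actors only ("Actors who simulate one of four psychiatric illnesses", or a control condition). Its fields (x) and (xi) record the medication and psychiatric treatment recommended at each interview.

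**The concern.** A component named in the primary outcome should correspond to a listed analysis with a defined comparator, case set and match rule. For treatment, following the SAP as written produces two accuracy figures and no agreement figure. This is more than missing detail, because the SAP states a comparator and it is not the one in the primary outcome.

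Two things could follow. The two gold-standard percentages could be read side by side as if they showed agreement. Or an agreement rate could be added later, with the match rule and the set of cases settled once the data are visible. Treatment recommendations can be lists (Appendix 2 has four medication lines and several psychotherapy options), so the choice of match rule can move the result a great deal.

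**Working it through.** The documents give no figure for treatment agreement, so there is none to reproduce. The check has three parts.

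**1. What each listed item compares**

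| SAP item | Domain | Liv vs gold standard | Psychiatrists vs gold standard | Liv vs psychiatrists |
|---|---|---|---|---|
| 1–4, repeated in 5–10 | Diagnosis | yes | yes | yes |
| 11–12 | Diagnosis with severity | yes | yes | yes |
| 13–15 | Severity | yes | yes | yes |
| 16 | Medication | yes | yes | **none** |
| 17 | Psychiatric treatment | yes | yes | **none** |
| Threshold A | Primary diagnosis | no | yes | no |
| Threshold B | Primary diagnosis | no | no | yes |

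Treatment is the only domain among items 1–17 without a direct comparison.

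**2. Whether items 16–17 determine agreement**

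Let *a* and *b* be the shares of the same cases in which Liv and the psychiatrist match the gold-standard drug G. The documents give no values, so those below are assumptions.

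*One drug per recommendation.* The two must agree wherever both name G, which is at least *a* + *b* − 1 of cases. They cannot agree where exactly one names G, which is at least |*a* − *b*| of cases. So agreement lies between max(0, *a* + *b* − 1) and 1 − |*a* − *b*|.

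- 80% each: 0.80 + 0.80 − 1 = 0.60, up to 1.00.
- 85% each: 0.85 + 0.85 − 1 = 0.70, up to 1.00.
- 90% and 70%: 0.90 + 0.70 − 1 = 0.60, up to 1 − 0.20 = 0.80.

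*Several drugs per recommendation, with credit for including G.* The range now depends on the match rule. Suppose that in every case the psychiatrist lists Y then G, and Liv lists X then G. Both score 100% against the gold standard. Yet first-listed agreement is 0%, the rule that Liv's list must contain the psychiatrist's first drug also gives 0%, and a rule that any shared drug counts gives 100%. Identical lists give 100% under all three rules.

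- First-listed versus first-listed: 0% to 100%, at 80% each as at 100% each.
- Any shared drug: both lists contain G in at least *a* + *b* − 1 of cases, so the floor is 60% at 80% each and 70% at 85% each.

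**3. The case set**

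Section (d) does not say whether the set of correct primary diagnoses is each interviewer's own or the set on which both are correct. If Liv and the psychiatrists were each right in 85% of matched cases (an assumption), the joint set would be between 0.85 + 0.85 − 1 = 0.70 and 0.85 of cases. With own sets, the two percentages in item 16 could therefore rest on partly different interviews. The primary-outcome paragraph contains no restriction to correct diagnoses.

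**The case against.** The strongest defence is one of scope. The SAP reads as the plan for the actor phase: its Data section covers actors, and section (e) uses the listed results to decide whether Liv proceeds to a Phase II study in patients. Actors have a defined truth, so scoring both interviewers against it is a sound choice. That stands, and items 16–17 should be kept. It does not supply the agreement rate that the primary outcome asks for, and the SAP lists direct comparisons for diagnosis and severity in the same actors.

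Three textual defences are also available.

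- Item 2 is worded generally. But it sits under (a) Diagnosis, and item 4 defines the agreement in terms of diagnoses.
- The word *main* leaves room for further treatment analyses. It does, but none is listed.
- Paragraph (f) might cover treatment. It does not appear in the text, so this cannot be excluded, but it is cited only for item 2.

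Some stronger readings are tempting and are not supported.

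- A reader might infer that the data for the comparison will not be collected. For actors they will be, in fields (x) and (xi).
- A reader might infer that percentages based on inclusion place no floor under agreement. That holds for first-listed rules and fails for an any-shared-drug rule.
- A reader might infer that the rule will be picked after the data are seen. The documents show only that it could be.
- A reader might treat the absence of any patient analysis as part of this defect. It is a separate and wider gap, which affects diagnosis and severity equally.

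**Conclusion.** The point holds as an omission from the analysis list. A named component of the primary outcome, treatment agreement between Liv and the psychiatrist, has no listed analysis, and items 16–17 cannot stand in for it. With one drug per recommendation on matched cases, 80% each against the gold standard is compatible with agreement from 60% to 100%, and 85% each with 70% to 100%. With multi-drug lists the range is 0% to 100% under first-listed matching, while an any-shared-drug rule keeps the floor at 60% (80% each). These rates are assumed, and the bounds apply to matched cases only. For actors, the SAP itself says that the Liv-versus-psychiatrist calculation needs a special method.

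A reader might infer that the decision to move to patients is compromised. It is not, because thresholds A and B rest on primary diagnosis alone. A reader might also be drawn to put an interval on the patient rate by spreading the 200 patients over the ten listed psychiatrists. No section says that those ten see all the patients, so that figure is not part of this conclusion.

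The change should be made before the data are analysed. It does not call the other listed analyses into question.

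**What to change.** - Add two items to section (d) alongside 16–17: Liv-versus-psychiatrist percentage agreement with a 95% confidence interval, one for medication and one for psychiatric treatment. State the case set for each.
- Preset the match rule on the pattern of items 2 and 4: primary versus primary, then a repeat in which Liv's list includes the psychiatrist's primary recommendation. State which listed medication counts as primary, since Appendix 2 numbers its four lines without ranking them, and how several psychotherapies are scored.
- For actors, use the same method as item 2, and put that method in the text.
- State whether the set for items 16–17 is each interviewer's own or joint.
- For the 200 patients, for whom no gold standard is described, use the same direct agreement paired within patient, with Liv's recommendation stored in the Appendix 2 fields.

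The cost is SAP wording, a few tables and storage of Liv's output for patients. Fields (i)–(xi) hold psychiatrist identity but not actor identity or day. Those must also be recorded if the actor interval is to allow for repeated actors, or if the comparison is limited to days with both interviewers.

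There are two downsides. Actor intervals will be wide: an assumed 80% agreement on the stated 50 psychiatrist encounters gives a Wilson interval of 67.0% to 88.8% before any allowance for repetition. That figure describes the added analysis, not the defect. An inclusion rule also favours longer lists, so the number of medications that Liv lists should be shown.
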